It is recognized that this is an extensive list of potential covariates with a limited sample size. Model selection will attempt forward or backward selection approaches to arrive at a parsimonious model. Results will be reported as odds ratios (ORs) with corresponding 2-sided 95% CIs. Effect modification/interaction will be tested for select variables (eg, vaccination status, colonization status, blood loss, units of transfusion). Results of the multivariable conditional logistical regression will be reported as odds ratios (ORs) with 95% confidence intervals (CIs). Frequency counts and summary statistics (n, mean, standard deviation, median, minimum, and maximum) will be compiled for serology results and all covariates listed above by case/control status.

Proportion of blood loss will be estimated from blood loss (ml) divided by the estimated preoperative blood volume. Estimation of preoperative blood volume depends on sex:

- Male: volume (mL) =  $(0.006012 \times H^3)/(14.6 \times W) + 604$
- Female: volume (mL) =  $(0.005835 \times H^3)/(15 \times W) + 183$
- where H = height in inches and W = weight in pounds.

Additional sensitivity analyses include 1) repeating overall model for STRIVE primary endpoints only, 2) excluding controls with other non-*S. aureus* infections, and 3) limiting analysis to per protocol subjects.

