- Subjects with any postoperative *S aureus* BSI and/or deep incisional or organ/space SSI occurring within 90 days of the index surgery, limited to unscheduled blood draws within 90 days
- Subjects with any postoperative *S aureus* BSI and/or deep incisional or organ/space SSI occurring within 180 days of the index surgery, limited to unscheduled blood draws within 180 days
- Subjects with any postoperative *S aureus* SSI within 90 days of the index surgery, limited to unscheduled blood draws within 90 days
- Subjects with any postoperative *S aureus* SSI within 180 days of the index surgery, limited to unscheduled blood draws within 180 days
- Subjects with any adjudicated postoperative ISA disease within 90 days of the index surgery, limited to unscheduled blood draws within 90 days
- Subjects with any adjudicated postoperative ISA disease within 180 days of the index surgery, limited to unscheduled blood draws within 180 days

Subjects with more than 1 endpoint of unplanned BSI/SSI assessment will participate in each relevant analysis.

If a specific unscheduled assessment visit was not done, serology samples collected at scheduled visits occurring within 7 days before or after the onset of a PDI may be used in these analyses.

Two additional analyses using ANCOVA will be performed to assess the association between absolute functional antibody levels (at V1 versus V2, V2 versus V2 discharge) and possible interfering host factors, include interaction terms.

1) *ANCOVA comparing V1 versus V2 admission*: This sub-analysis will be limited to those with serological testing at V1 which includes 51 cases and a subset of ~50 controls (chosen from among the 2 vaccinated controls per vaccinated case matched by site). Least-squares means (LSMs) and associated CIs for both vaccine groups at each postbaseline visit will be estimated from an analysis of covariance (ANCOVA). The dependent variable will be log V2 admission titer minus log day-of-vaccination (V1) titer. The model terms will be vaccine group, site, demographics (age, sex, race/ethnicity, BMI, ASA, CCI), colonization status at V1, diabetes, smoking status and elapsed number of days from V1 to V2 admission. Colonization status will be based on any *S aureus* at V1 and will be defined as positive if either nose or throat is positive; otherwise, it will be defined as negative.

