Type 3 sums of squares will be used. The difference between SA4Ag and placebo in LSMs will be obtained for V1 versus V2 admission. The exponentiated differences will be ratios of the vaccine groups' geometric means. The corresponding 2-sided 95% CIs will be obtained.

*ANCOVA comparing V2 admission versus V2 discharge*: An exploratory analysis of effect of blood loss on immunogenicity will be performed. This sub-analysis will include subjects with serological testing at both V2 admission and discharge which includes 51 cases and 357 controls. Loss of titer is assumed to be proportional to blood loss divided by the estimated preoperative blood volume. Assay titers will be log transformed. The dependent variable will be log day-of-discharge titer minus log day-of-surgery titer. If a subject has more than 1 set of relevant immunogenicity results after the index surgery, the earliest results will be used.

The statistical model will be ANCOVA. The model terms will be vaccine group, site, colonization status at V1/V2, , demographics (age, sex, race/ethnicity, BMI, ASA, CCI), diabetes, smoking status, elapsed number of days from the day of surgery to the day of discharge (calculated as the day of discharge minus the day of surgery, plus 1), proportion of blood loss (%), transfusion volume (mL), presence of specific types of transfusion (packed RBCs, platelets, whole blood and plasma), origin of blood product (heterologous or autologous, limited to subjects with packed RBCs or whole-blood transfusion), cell saver, case status and case status by vaccine group interaction. Colonization status will be based on any *S aureus* at V1 or V2 admission and will be defined as positive if either nose or throat is positive; otherwise, it will be defined as negative.

Other terms may be explored. Geometric means will be estimated for levels of statistically significant factors.

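### As printed, the blood-volume equations give about 605 mL for every man and 184 mL for every woman, so the blood-loss percentage is raw mL on two sex scales that do not match

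*SAP*

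**What the plan says.** SAP section 8.1.3.5 replaces all earlier immunogenicity plans after the study met its futility criteria in December 2018. Under Objective 1 it defines a covariate: "Proportion of blood loss will be estimated from blood loss (ml) divided by the estimated preoperative blood volume". Two equations for preoperative volume in mL follow, "where H = height in inches and W = weight in pounds":

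- Men: (0.006012 × H³)/(14.6 × W) + 604
- Women: (0.005835 × H³)/(15 × W) + 183

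The SAP cites its reference 11 for these. It gives no worked volume and no plausible range, and no other section gives a different equation.

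The resulting percentage is used in two places, both repeated in Table 26:

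- **Objective 1 conditional logistic regression.** It is one of many candidate covariates. "Model selection will attempt forward or backward selection approaches to arrive at a parsimonious model". Whatever selection retains, summary statistics "will be compiled for serology results and all covariates listed above by case/control status". Blood loss is also named as a variable for effect-modification testing, without saying whether in mL or as the percentage.
- **Objective 2 ANCOVA, Visit 2 admission to discharge.** This is an exploratory analysis of the effect of blood loss on titer. Its premise is: "Loss of titer is assumed to be proportional to blood loss divided by the estimated preoperative blood volume".

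**The concern.** Dividing by blood volume is meant to express a loss relative to the size of the patient. That requires a denominator that varies with height and weight and has the magnitude of a human blood volume. In the printed form, height and weight enter only through a quotient that looks negligible beside the added constant. If so, the denominator is a fixed number for each sex, and the numbers for men and women differ by a factor of about three.

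The ANCOVA is the more exposed analysis, because the percentage is its exposure of interest. In Objective 1 the percentage is an adjustment variable, but its values will still be tabulated for cases and controls.

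**Working it through.** **Inputs.** The equations and units are those in SAP section 8.1.3.5. The documents give no height, weight or blood-loss distribution, so the body sizes are assumptions: six example patients, plus a grid of 56 to 80 in by 90 to 350 lb. There is no SAP figure to reproduce.

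**Step 1: one patient of each sex.**

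- Man, 70 in, 180 lb: 0.006012 × 343,000 = 2062.1; 14.6 × 180 = 2628; 2062.1/2628 = 0.78; plus 604 = 604.8 mL.
- Woman, 64 in, 160 lb: 0.005835 × 262,144 = 1529.6; 15 × 160 = 2400; 1529.6/2400 = 0.64; plus 183 = 183.6 mL.

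**Step 2: other body sizes.** The last two columns replace the division by addition. That form is inferred from plausibility only and is shown for contrast.

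| Patient | Volume as printed (mL) | 500 mL loss as printed | Volume with addition (mL) | 500 mL loss with addition |
|---|---|---|---|---|
| Man 64 in, 130 lb | 604.8 | 82.7% | 4078 | 12.3% |
| Man 76 in, 280 lb | 604.7 | 82.7% | 7331 | 6.8% |
| Woman 60 in, 110 lb | 183.8 | 272.1% | 3093 | 16.2% |
| Woman 70 in, 250 lb | 183.5 | 272.4% | 5934 | 8.4% |

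**Step 3: whole grid.** The quotient runs from 0.20 to 2.34 mL. Volume is 604.2 to 606.3 mL in men (0.4% variation) and 183.2 to 185.2 mL in women (1.1%). The male-to-female ratio is 3.26 to 3.31. With BMI limited to 18 to 45, the quotient is 0.34 to 1.29 mL and the ratio 3.28 to 3.30. Volume also moves the wrong way with weight: a 68 in man falls from 605.0 mL at 130 lb to 604.4 mL at 330 lb.

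**Step 4: the scale.** The covariate is in effect 100 × mL/605 in men and 100 × mL/184 in women. Any loss above those volumes exceeds 100%. A 200 mL loss scores 33% in men and 109% in women.

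**Step 5: the fitted slope.** With one coefficient b per percentage point, the effect per mL is b × 100/604.8 = 0.165b in men and b × 100/183.6 = 0.545b in women. The ratio is 0.545/0.165 = 3.3. Sex as a main effect shifts the intercept and leaves this ratio in place.

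**Step 6: other readings of the printed line.** None gives a credible pair of volumes.

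- Metric units: 632 mL (man, 178 cm, 82 kg) and 208 mL (woman, 163 cm, 68 kg).
- Ignoring the second bracket, so that the quotient is multiplied by weight: 26,027 mL (man, 70 in, 180 lb) and 15,479 mL (woman, 64 in, 150 lb).
- Moving the constant into the denominator: 0.6 mL (man, 70 in, 180 lb).

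**The case against.** **The operator may be a reading error.** The point turns on one character per line in machine-read mathematics, and an additive form would carry the same brackets. Both lines passed through the same reader, so their agreement is weak support. This stands as a limit: the finding is certain for the text as it reads and needs confirming in the source SAP. Nothing in the documents suggests that the slash was misread.

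**No effect on a reported estimate is shown.** The figures describe the covariate; no odds ratio or titer ratio has been recalculated. Within a sex the printed form is nearly a linear rescaling of mL, so it still adjusts for blood loss in part. In Objective 1 it may be dropped by selection, and sex and BMI are listed covariates. All of this is fair for Objective 1. It does not rescue the ANCOVA, where the percentage is the exposure. Additive sex and BMI terms do not rescale blood loss.

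**Further terms are allowed.** The SAP presents the two ANCOVAs as looking at "possible interfering host factors, include interaction terms", and adds "Other terms may be explored". But the only interaction named for the admission-to-discharge model is in "case status and case status by vaccine group interaction". A sex-by-blood-loss term would free the two slopes without restoring the body-size adjustment or a valid percentage.

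**The planned summaries would expose it.** Minimum and maximum values are to be tabulated, so results in the hundreds of percent would be visible. The SAP does not say that anyone reviews them before the models are fitted.

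**The program may already be right.** The documents cannot show this either way.

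**Conclusion.** The concern holds as printed. Followed literally, the equations give a near-constant denominator for each sex, with about a 3.3-fold difference between the sexes. The covariate loses its body-size adjustment, its percentage meaning and its comparability between men and women. The volumes rest on the assumed body-size ranges, but the quotient is so small that any adult range gives the same conclusion.

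The consequence is confined to exploratory, post-futility immunogenicity work. The admission-to-discharge ANCOVA is affected directly, as are the Objective 1 covariate summaries. The Objective 1 model is affected if blood loss survives selection, and its effect-modification test is affected if that test uses the percentage. SAP section 6.4 proposes no covariates for the primary and secondary efficacy analyses, so the trial's efficacy conclusion is not touched. This should be fixed because a programmer following the SAP would produce an exposure that cannot be interpreted.

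**What to change.** 1. Confirm the operator in both equations in the source SAP.
2. Reconcile both equations and the analysis program with the SAP's reference 11. Replacing division by addition gives litre-scale volumes (5294 mL for the 70 in, 180 lb man), but that form is inferred here and must be taken from the reference.
3. Add a range check on derived blood volume, by sex, before either model is fitted.
4. State whether the Objective 1 effect-modification test uses mL or the percentage.

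If the additive form is confirmed, the correction is one operator in each of two equations, plus a derivation check and one clarifying sentence. No new data are needed.

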#### *Objective 2:*

Tabular summaries and graphical displays of serological results by case/control status and vaccination status at each sampling time point will be generated. The immunogenicity baseline will be the Visit 1 prevaccination blood draw. Assay values from sera obtained up to 7 days before vaccination will be considered eligible for analysis.

The number and proportion of subjects achieving threshold values will be obtained at each scheduled time point for vaccine group. Threshold values are identified in [Table 8](#). Two-sided 95% CIs will be compiled. Comparisons will be conducted by vaccination and case status (ie, placebo-case, placebo-noncase, SA4Ag-case, and SA4Ag-noncase) using the Fisher exact test, 2-sided.

Vaccine groups will be summarized by proportion of subjects achieving each of 4 thresholds simultaneously. The 4 antigens will be CP5/OPA, CP8/OPA, ClfA/cLIA, and MntC/cLIA. These proportions will be compiled for each scheduled visit. Two-sided 95% CIs will be compiled for each proportion. The vaccine groups will be compared using the Fisher exact test, 2-sided.

GMTs at select time points (V1, V2, V2 discharge, V5, and unscheduled BSI/SSI visits) are obtained by log transformations of indicated values, averaging the log values, then exponentiating the result. The associated 2-sided 95% CI will be obtained by calculating the CI in log scale, referencing the t-distribution, and then exponentiating the lower and upper limits.

GMFRs are geometric means of the titer from the indicated visit divided by the corresponding baseline titer. Subjects missing either baseline or the applicable visit titer are excluded from the calculation. GMTs, GMFRs, and their 2-sided 95% CIs will be calculated for each scheduled time point.

GMTs, GMFRs, and their associated 2-sided 95% CIs will be calculated again for each select time point, but the statistics will be obtained for vaccine group and case occurrence (yes/no), ie, placebo-case, placebo-noncase, SA4Ag-case, and SA4Ag-noncase. These time profiles will be compiled for BSI cases, SSI cases, and ISA cases. Subjects who have more than 1 type of case will appear in as many case categories as relevant. Profiles will be calculated for all time points up to 90 days. Titers obtained after case onset will be excluded, so sample sizes for cases will shrink over time.

GMTs and GMFRs will also be obtained for the following subjects with unscheduled BSI/SSI visits:

- Subjects with any postoperative *S aureus* BSI and/or deep incisional or organ/space SSI occurring within 90 days of the index surgery, limited to unscheduled blood draws within 90 days
- Subjects with any postoperative *S aureus* BSI and/or deep incisional or organ/space SSI occurring within 180 days of the index surgery, limited to unscheduled blood draws within 180 days
- Subjects with any postoperative *S aureus* SSI within 90 days of the index surgery, limited to unscheduled blood draws within 90 days
- Subjects with any postoperative *S aureus* SSI within 180 days of the index surgery, limited to unscheduled blood draws within 180 days
- Subjects with any adjudicated postoperative ISA disease within 90 days of the index surgery, limited to unscheduled blood draws within 90 days
- Subjects with any adjudicated postoperative ISA disease within 180 days of the index surgery, limited to unscheduled blood draws within 180 days

Subjects with more than 1 endpoint of unplanned BSI/SSI assessment will participate in each relevant analysis.

If a specific unscheduled assessment visit was not done, serology samples collected at scheduled visits occurring within 7 days before or after the onset of a PDI may be used in these analyses.

Two additional analyses using ANCOVA will be performed to assess the association between absolute functional antibody levels (at V1 versus V2, V2 versus V2 discharge) and possible interfering host factors, include interaction terms.

1) *ANCOVA comparing V1 versus V2 admission*: This sub-analysis will be limited to those with serological testing at V1 which includes 51 cases and a subset of ~50 controls (chosen from among the 2 vaccinated controls per vaccinated case matched by site). Least-squares means (LSMs) and associated CIs for both vaccine groups at each postbaseline visit will be estimated from an analysis of covariance (ANCOVA). The dependent variable will be log V2 admission titer minus log day-of-vaccination (V1) titer. The model terms will be vaccine group, site, demographics (age, sex, race/ethnicity, BMI, ASA, CCI), colonization status at V1, diabetes, smoking status and elapsed number of days from V1 to V2 admission. Colonization status will be based on any *S aureus* at V1 and will be defined as positive if either nose or throat is positive; otherwise, it will be defined as negative.

Type 3 sums of squares will be used. The difference between SA4Ag and placebo in LSMs will be obtained for V1 versus V2 admission. The exponentiated differences will be ratios of the vaccine groups' geometric means. The corresponding 2-sided 95% CIs will be obtained.

*ANCOVA comparing V2 admission versus V2 discharge*: An exploratory analysis of effect of blood loss on immunogenicity will be performed. This sub-analysis will include subjects with serological testing at both V2 admission and discharge which includes 51 cases and 357 controls. Loss of titer is assumed to be proportional to blood loss divided by the estimated preoperative blood volume. Assay titers will be log transformed. The dependent variable will be log day-of-discharge titer minus log day-of-surgery titer. If a subject has more than 1 set of relevant immunogenicity results after the index surgery, the earliest results will be used.

The statistical model will be ANCOVA. The model terms will be vaccine group, site, colonization status at V1/V2, , demographics (age, sex, race/ethnicity, BMI, ASA, CCI), diabetes, smoking status, elapsed number of days from the day of surgery to the day of discharge (calculated as the day of discharge minus the day of surgery, plus 1), proportion of blood loss (%), transfusion volume (mL), presence of specific types of transfusion (packed RBCs, platelets, whole blood and plasma), origin of blood product (heterologous or autologous, limited to subjects with packed RBCs or whole-blood transfusion), cell saver, case status and case status by vaccine group interaction. Colonization status will be based on any *S aureus* at V1 or V2 admission and will be defined as positive if either nose or throat is positive; otherwise, it will be defined as negative.

Other terms may be explored. Geometric means will be estimated for levels of statistically significant factors.

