The interim analysis will be performed on the first 24 PP cases and the final analysis will be performed on the first 48 PP cases. Although the final analysis is expected to have 48 cases, it is possible that additional potential cases will be present in the adjudication system (entered into the adjudication electronic case report form [eCRF]) on the same day that the 48th per-protocol case is reported to the EAC. These additional cases will be included in the final analysis, if confirmed as cases by the EAC. Therefore, the time order of case notification from the EAC to the sponsor will determine which cases will be included in the analysis. O'Brien-Fleming boundaries will be maintained for decisions regarding VE.

O'Brien-Fleming boundaries will also be maintained if the EAC informs the sponsor of the 25th case (or any further cases) on the same day. It is possible that additional potential cases will be present in the adjudication system. The time order of case notification from the EAC to the sponsor will determine which cases will be included in the interim analysis. Even if more than 24 cases are included in the interim analysis, the final analysis will be performed on 48 cases, unless additional cases are available as described in this section.

The interim analysis will not be revised even if the interim and final case counts do not meet planned values; eg, if the interim analysis is performed with 24 cases, but the final PP analysis has 49 or more cases, the interim analysis will not be revised.

Only the primary endpoint in the PP efficacy population will be subjected to an interim analysis.

The futility analysis will be applied to the primary endpoint only, in the PP efficacy population. After accumulating approximately 10, 15, and 24 primary endpoint cases, the power of the study to reject the original null hypothesis, conditional upon the results accumulated so far, will be calculated. Futility may be declared and the study may cease enrollment, if the conditional power falls below 20%. This will occur if 7 or more vaccine cases are observed out of 10 total cases at the first futility check, or if 9 or more vaccine cases are observed out of 15 total cases at the second futility check, or if 11 or more vaccine cases are observed out of 24 total cases at the third futility check.

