### **8.1.3.5. Immunogenicity**

On December 20, 2018, the STRIVE study met its pre-specified futility criteria at its Interim Analysis and ceased enrollment. The rationale for this change in immunogenicity testing and analysis is to focus efforts on improving our understanding of why the vaccine did not appear to prevent post-operative *S. aureus* infections. This analysis will replace all previously planned immunogenicity analyses.

The immunogenicity testing and analysis will focus on the four objectives listed below:

Primary objective:

1. To assess the association between CP5/8, ClfA, and MntC functional antibody levels and *S. aureus* infections among subjects within the STRIVE study, adjusting for demographics, health status, and surgical characteristics

Secondary objective:

2. To describe the CP5/8, ClfA, and MntC functional antibody levels among surgical subjects at selected time points by case and vaccination status

Exploratory objectives:

3. To compare the functional immune response to CP5/8, ClfA, and MntC among vaccinated surgical subjects without *S. aureus* infection with vaccinated healthy (non-surgical) subjects
4. To compare the functional immune response of CP5/8, ClfA, and MntC at unscheduled BSI/SSI visit among subjects with *S. aureus* infection with scheduled visits of similar time intervals among subjects without *S. aureus* infection

Study Design:

A nested case-control study within the STRIVE study will be conducted to assess the association of *S. aureus* infection and immunogenicity endpoints at select timepoints, adjusting for demographics, health status, and surgical characteristics. Cases and controls will be matched by study site.

Cases will be any subjects (per protocol or mITT) with adjudication-confirmed *S. aureus*-related SSI and/or BSI (includes deep, organ/space and superficial SSIs). Infections with positive *S. aureus* cultures deemed not clinically significant by adjudicators will be excluded. Other invasive *S. aureus* infections will have descriptive analysis separate from objective 1 and without matched controls. At this time, there are 5 such cases: additional cases may be identified prior to study closeout.

Controls will be per protocol subjects from same study site as cases who completed Visit 5 (post-op Day 90) but did not develop adjudication-confirmed *S. aureus* infections. A total of 7 controls will be selected per case (5 vaccinated and 2 unvaccinated controls per case).

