At this time, the plan is to include a total of 51 cases of *S. aureus* infection (both SA4Ag vaccinated and placebo) and 357 controls will be included in this sub-analysis. For the few sites with a shortfall in available controls due to low enrollment, remaining controls will be randomly selected from other “case” sites (ie, sites with cases that have unselected controls remaining) to meet control targets. Extra controls will be associated with their actual site in the logistic regression analysis.

Data analysis:

All analyses will be performed for CP5/OPA, CP8/OPA, ClfA/cLIA, and MntC/cLIA.

*Objective 1:*

The key independent variables of interest are CP5 and CP8 functional antibody levels (as measured by OPA assay), and secondary independent variables include ClfA and MntC antibody levels (as measured by cLIA assay) assessed at the following time points.

The primary analysis will include the following immunogenicity variables (one value for each antigen for each specimen):

- Day of index surgery before surgery (V2 admission) log transformed titers
- V2 hospital discharge log transformed titers minus V2 admission log transformed titers [Quantify change from V2 admission]
- V5 post-op day 90 log transformed titers minus V2 hospital discharge log transformed titers [Quantify change from V2 discharge]

Multivariate conditional logistic regression will be conducted to model the odds of *S. aureus* infection based on functional antibody levels (ie, 3 immunogenicity variables based on V2 and V5 described above), adjusting for following covariates:

- Demographics (age, sex, race/ethnicity, BMI, ASA, CCI)
- Operative time (mins)
- Number of motion segments/intervertebral levels fused
- Proportion of blood loss (%)
- Units of transfusion
- Days from vaccination to surgery
- Days from surgery to discharge
- Primary versus revision spinal fusion surgery
- Season/year of surgery
- Colonization status (IHMA swab results)
- Diabetes
- Smoking status
- Intrawound antibiotic use (eg, vancomycin vs. other vs. none)

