## Descriptive Figures

Descriptive figures will be generated for immunogenicity. Each antigen-assay combination will be presented in a separate figure. The legend will identify SA4Ag and placebo, except as noted. All scales for antigen titers and geometric means will be log scales. Plots will be generated for the mITT immunogenicity population.

1. Reverse cumulative distribution curves (RCDCs) will be generated for the day of vaccination, the day of surgery, the day of discharge and Day 90.
2. Titers from the day of index surgery will be plotted against elapsed days from the day of vaccination to the day of the index surgery. The purpose is to profile titer distribution before surgery for a variety of days since vaccination.
3. GMTs and their 95% CIs will be plotted against time point to create kinetic plots. The time points will be labeled “Day of Vaccination,” “Day of Surgery,” “Day of Discharge,” and “Day 90,”.

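### By-arm immunogenicity displays in SAP 8.1.3.5 pool cases and controls from a case-enriched sample, and placebo outputs that need a Visit 1 titer rest on infected cases alone

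*SAP*

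**What the plan says.** SAP 8.1.3.5 replaces all earlier immunogenicity plans with a nested case-control study. On cases: "Cases will be any subjects (per protocol or mITT) with adjudication-confirmed *S. aureus*-related SSI and/or BSI", superficial infections included. On controls: "A total of 7 controls will be selected per case (5 vaccinated and 2 unvaccinated controls per case"). Controls must be per-protocol, have completed Visit 5 (V5, Day 90) and come from sites with cases. On size, "the plan is to include a total of 51 cases of *S. aureus* infection (both SA4Ag vaccinated and placebo) and 357 controls".

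The mITT immunogenicity population (SAP 5.4.1) is every vaccinated subject with at least one valid postvaccination result, and Table 26 uses it for every immunogenicity analysis. Objective 2 defines a GMT as the exponentiated plain mean of log titers and states: "GMTs, GMFRs, and their 2-sided 95% CIs will be calculated for each scheduled time point". It reports threshold proportions by vaccine group and compares the vaccine groups by Fisher test on meeting all four thresholds at once. For the RCDCs and kinetic plots, SAP 8.2.3.5 says: "The legend will identify SA4Ag and placebo, except as noted".

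Objective 2 then repeats GMTs and GMFRs by arm and case status. In that paragraph stands the only exclusion of late samples: "Titers obtained after case onset will be excluded, so sample sizes for cases will shrink over time".

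For Visit 1 (V1, before vaccination), Table 13 gives titers for all cases but for only about 50 controls, and its footnote says that these are vaccinated. The ANCOVA text under Objective 2 agrees. Table 8 defines the ClfA and MntC thresholds as at least a 4-fold rise from V1.

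**The concern.** A sample built to contain every case and a few controls does not have the trial's mix of subjects. A summary by arm that ignores the sampling describes that artificial mix. Placebo contributes 2 controls per case against 5 for SA4Ag, so cases weigh more in the placebo summaries and the distortion need not cancel in the contrast.

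Two consequences follow. At Day 90, titers drawn after an infection could reflect the infection itself. For anything that needs a baseline, the placebo group has no uninfected members at all. These displays are the plan's remaining by-arm answer to the exploratory objective of describing SA4Ag immunogenicity in surgical patients (Protocol 2.4).

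**Working it through.** **Inputs.** 51 cases; 5 SA4Ag and 2 placebo controls per case (SAP 8.1.3.5); expected case incidence of 1.4% or less (SAP 8.1.1). The split of cases by arm is not stated. The study stopped for futility, which at the third check occurs "if 11 or more vaccine cases are observed out of 24 total cases at the third futility check". With exactly 24 cases, at most 13 of 24 (54%) were then placebo. I assume 20 to 31 placebo cases among the 51, with an even split as the central value.

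**The plan's own figure.** 51 × (5 + 2) = 357 controls, as stated. By arm: 51 × 5 = 255 SA4Ag and 51 × 2 = 102 placebo.

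**Case share at V2 admission, V2 discharge and V5** = arm cases / (arm cases + arm controls).

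| Placebo cases | Placebo share | SA4Ag share | Ratio of shares |
|---|---|---|---|
| 20 | 20/122 = 16.4% | 31/286 = 10.8% | 1.5 |
| 25.5 (even) | 25.5/127.5 = 20.0% | 25.5/280.5 = 9.1% | 2.2 |
| 31 | 31/133 = 23.3% | 20/275 = 7.3% | 3.2 |

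With the 62 cases and 350 controls of Table 13, split evenly, the shares are 31/131 = 23.7% and 31/281 = 11.0%.

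**Effect on a Day 90 placebo GMT if samples taken after onset are kept.** If a share *w* of subjects has titers *F* times those of the rest, the pooled GMT is multiplied by *F^w*. The documents give no *F*, so the values below are assumptions.

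| Assumed rise *F* | *w* = 16.4% | *w* = 20.0% | *w* = 23.3% |
|---|---|---|---|
| 1 | 1.00 | 1.00 | 1.00 |
| 2 | 1.12 | 1.15 | 1.18 |
| 4 | 1.26 | 1.32 | 1.38 |
| 10 | 1.46 | 1.58 | 1.71 |

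For a given *F* and *w* these are upper bounds: the formula treats every case as already infected at Day 90, and a case with later onset adds no postinfection titer. If samples taken after onset are excluded, the factor is about 1.00.

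**Outputs that need V1.** The number of placebo controls tested at V1 is 0, so the placebo case share is 25.5/25.5 = 100%, whatever the split. In SA4Ag it is about 25.5/(25.5 + 50) = 34%. The consequences need no assumption about titers:
- GMFRs exclude subjects without a baseline, so placebo GMFRs and n-fold rises come from cases only.
- No placebo control can be scored on the ClfA or MntC threshold, nor therefore on all four antigens. The 4-antigen Fisher test sets placebo cases against a mix of SA4Ag cases and controls.
- The placebo V1 RCDC and first kinetic point are all cases, while later points are about one fifth cases, so the subjects behind the curve change.

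**The case against.** Much of what is needed is already planned. Objective 2 promises summaries by case and vaccination status, repeats GMTs and GMFRs in the four arm-by-case groups, and in its text runs the single-threshold Fisher comparisons across those groups. Only the 4-antigen comparison is pooled there, although Table 26 lists plain vaccine group for both threshold analyses. This stands and limits the harm. It does not remove the pooled displays, and no case split is stated for the 4-antigen proportions, RCDCs or kinetic plots.

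A reader might infer that Day 90 placebo titers are inflated, or that the SA4Ag/placebo ratio is shrunk. The documents support neither. They report no titers and no rise after infection, and the ratio would also need the rise in each arm. Nor do they say that the onset rule stops at the case-split profiles: it is written there, and its reach is left open.

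The comparison with 1.4% is not like for like. That figure is the expected incidence quoted for the primary endpoint, whereas the 51 cases include superficial infections and mITT subjects. The futility result concerns per-protocol primary-endpoint cases and makes a near-even split plausible without establishing it. The counts also disagree: 51 cases in the text against 50 in Table 12, 357 controls against 350 in Table 13, and for other invasive infections "At this time, there are 5 such cases: additional cases may be identified prior to study closeout", against 12 in Table 12. None of this brings the case share near the trial's own.

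Inverse-sampling weights within arm look like the natural remedy. They would not recover the trial population, because subjects at sites without cases, and those who were not per-protocol Visit 5 completers, could not be drawn as controls.

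**Conclusion.** The point holds as a defect of the by-arm displays. They pool a case-enriched sample without weights or restriction. Cases form about 16-23% of tested placebo subjects and 7-11% of tested SA4Ag subjects at V2 admission, V2 discharge and V5, roughly a twofold difference between arms at an even split. These shares rest on 20 to 31 placebo cases among 51. Inflation of Day 90 placebo titers is possible, not shown: at a 20% case share at most about 1.15, 1.32 or 1.58 times for an assumed 2-, 4- or 10-fold rise, and none if samples taken after onset are dropped.

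The finding on V1 is firmer. It rests only on reading vaccinated in Table 13 as SA4Ag, as the section's contrast with unvaccinated controls indicates. Placebo V1 GMTs, GMFRs, n-fold rises, ClfA/MntC thresholds and the 4-antigen proportion then come entirely from infected cases.

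A reader should not carry this over to vaccine efficacy. The analyses are exploratory, follow the futility stop, and leave the efficacy conclusion unaffected.

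**What to change.** In SAP 8.1.3.5 Objective 2, Table 26 and the Descriptive Figures:

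- Compute by-arm GMTs, CP5 and CP8 threshold proportions, RCDCs and kinetic plots at V2 admission, V2 discharge and V5 in noncase controls only, labelled as per-protocol controls from sites with cases. Show cases only in the case-split displays.
- Apply the exclusion of titers after case onset to every display by vaccine group that includes cases, other than the unscheduled BSI/SSI visit analyses.
- For outputs that need V1 (GMFR, n-fold rise, ClfA/MntC threshold, 4-antigen proportion, V1 RCDC and V1 kinetic point), drop the SA4Ag-versus-placebo comparison or label the placebo values as cases only. A noncase filter cannot rescue them, since it leaves no placebo subjects.
- Do not use inverse-sampling weights within arm.

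The cost is SAP wording and a population filter. By-arm sample sizes fall by the cases, to 102 placebo and 255 SA4Ag controls as planned, and the placebo fold-rise comparison is lost.
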